The primary objective is to evaluate response to therapy (defined as complete, or partial response, and progression-free survival) in subjects with refractory or relapsed CLL who have relapsed after at least one prior therapy.

Secondary objectives are to evaluate toxicity, overall survival (OS), and complement levels (CH20 and C2) in subjects with refractory or relapsed CLL.

Study Design

This is an open-label, Phase II study of the combination of ofatumumab and fresh frozen plasma (FFP) in patients with relapsed or refractory CLL.

Approximately 12 subjects will be enrolled.

Treatment: 12 doses of ofatumumab as currently approved over a 24 week period with 2 units of FFP with each dose (with the exception of the first dose).

Patients will be followed for 2 years after the last dose of ofatumumab.

1.0 STUDY OBJECTIVES

Primary Objective:

- To evaluate the response to therapy (complete response (CR), or partial response (PR), and progression-free survival (PFS)) of subjects with refractory or relapsed CLL who have relapsed after at least one prior therapy.

Secondary Objectives:

- To determine the toxicity and safety of administration of the combination of ofatumumab and FFP
- To evaluate overall survival
- To evaluate complement levels in subjects with CLL receiving ofatumumab before and after the administration of FFP

2.0 BACKGROUND AND RATIONALE

2.1 Chronic Lymphocytic Leukemia (CLL)

Chronic Lymphocytic Leukemia is the most common type of leukemia in the Western world, accounting for 40% of all leukemia types in people over the age of 65 [Oscier, 2004]. It is estimated that in the US alone 15,110 adults (8,750 men and 6,360 women) were diagnosed and 4,390 adults will die of CLL in 2008 [Jemal, 2008]. The prevalence of CLL increases with age and the median age at the time of diagnosis is 65 to 70 years [Redaelli, 2004]. Approximately 50% of patients are initially asymptomatic and are observed for several years before treatment is needed, therefore more than half of patients who finally require therapy are older than 70 years. The disease is a hematological neoplasm of unknown etiology, characterized by accumulation of monomorphic small, round mature-appearing B lymphocytes in the peripheral blood, bone marrow, and lymph nodes that aberrantly co-express T-cell (CD5+) and B-cell (CD19+, CD23+) cell surface markers, with a low expression of CD20. Over the past decade, new information suggests B-CLL originates from antigen-stimulated mature B-lymphocytes, which either avoid cell death through the effect of external signals, or die by apoptosis, but are replenished by proliferating precursor cells [Chiorazz, 2005]. CLL follows a variable clinical course with overall survival times ranging from months to decades. Median survival from diagnosis is approximately 10 years in the overall CLL population, but is only 18 months for patients with advanced disease [Nabhan, 2004]; and 9-13 months for CLL cases refractory to fludarabine [Byrd, 2004].

Clinical staging systems devised by Rai and Binet are the best validated for evaluating CLL patients [Rai, 1975; Binet, 1981]; however, there is heterogeneity in the course of the disease within defined stages. In recent years, molecular and cellular markers have been correlated with disease aggressiveness. These allow further stratification of subjects into risk groups such as: abnormal cytogenetics, CD38, ZAP-70, beta-2-microglobulin, IgVH mutational status [Oscier, 2004; Abbott, 2006; Shanafelt, 2007; Zenz, 2007]. Unfortunately, so far, these parameters have only limited use in determining when and what type of therapy to use [Binet, 2006]. One exception is that p53 deletion was shown to be predictive for non-response to purine analogues like fludarabine and for poor clinical outcome, but is not predictive for response to a particular therapy [Dohner, 1995].

2.2 Current Treatment for CLL

Over the last two decades, the treatment goal of CLL has undergone a paradigm shift changing from simple symptom palliation to attainment of maximal disease control and consequently prolonged survival [Tam, 2007]. Clinical trials assessing single agent chemotherapy were followed by studies investigating combination chemotherapies which showed no significant difference in overall survival [Shanafelt, 2007]. Subjects receiving monotherapy or combination chemotherapy experience a range of different levels of toxicity [Abbott, 2006]. Currently, fludarabine and cyclophosphamide combined with Rituxan (FCR) seems to be the most potent regimen, both in previously untreated and relapsed patients [Hallek, 2008; Tam 2008]. In general, as with most clinical studies, all these trials endorse strict eligibility criteria often excluding subjects older than 65 plus those with inferior organ function. This causes a limitation in assessing the suitability of these studied therapy regimens regarding their efficacy and tolerability for the treatment of unselected patients in practice of which the majority is older and in poor health.

Despite numerous studies with various therapies demonstrating overall and complete response rates in both previously untreated and relapsed or refractory CLL patients [Hallek, 2001; Huhn, 2001; O'Brien, 2001a; O'Brien, 2001b; Keating, 2002; Wierda, 2005], there is no curative treatment and the disease often relapses. There is no current maintenance therapy to extend the time between relapses.

The biological behavior of CLL is similar to follicular lymphoma (FL), wherein the disease is incurable and the clinical course is characterized by a high relapse rate. After relapse, both the response rate and progression-free survival after subsequent salvage regimens steadily decrease [Montoto, 2002]. Recently, in relapsed FL patients, maintenance treatment with the chimeric CD20 mAb, rituximab, resulted in a median PFS of 51.5 months versus 14.9 months with observation only ($p<.001$). Significantly improved PFS was noted regardless of induction treatment (CHOP vs R-CHOP). Additionally, rituximab maintenance also improved overall survival at 3 years (85% vs 77%, $p=.011$) [van Oers, 2006]. Similar results of improved PFS and overall survival with rituximab maintenance in FL patients have been noted [Forstpointner, 2006; Hochster, 2009].

While rituximab monotherapy is not very effective in previously untreated or relapsed CLL patients, possibly due to the relatively low CD20 expression on CLL cells [Byrd, 2001], a recent small phase II study with rituximab consolidation and maintenance treatment showed a significantly longer response duration in patients with minimal residual disease (MRD)-positive CLL in first remission after fludarabine induction [Del Poeta, 2008].

2.3 Ofatumumab

Ofatumumab is a fully human monoclonal antibody (mAb), IgG1κ, targeting a unique epitope on the CD20 molecule expressed on human B-cells, resulting in increased binding affinity to CD20, prolonged dissociation rate, and increased cell kill due to greater complement dependent cytotoxicity (CDC) activity and similar antibody dependent cell mediated cytotoxicity (ADCC) activity, especially in low CD20 expressing cells [Teeling, 2006]. Thus, depletion of B-cells by ofatumumab treatment may provide clinical benefits to subjects with CD20-expressing cell tumors. In B-CLL, the goal of treatment is to achieve complete abnormal B-cell depletion in the blood and to induce an objective tumor response in the lymph nodes.

In a Phase I dose-ranging trial of ofatumumab 500mg (n=3), 1000mg (n=3), or 2000mg (n=27) given weekly x 4, 50% PR was observed in the 2000mg dose amongst relapsed CLL patients [Coiffier, 2008]. Objective response significantly correlated with maximum observed concentration (Cmax), minimum observed concentration (Cmin), area under the concentration-time curve (AUC), and half-life ($t^{1/2}$) and survival endpoints correlated with exposure. The maximum tolerated dose (MTD) was not reached and

treatment was well tolerated. Adverse events were limited to grade 1-2 infusion reactions and easily managed with premedication. Grade 3-4 neutropenia occurred in only 6% of patients. Non-opportunistic grade 1-2 infections were observed in 51% of patients.

Interim analysis for the pivotal trial evaluated 154 patients with refractory CLL (Study Hx-CD20-406). In the 138 evaluable patients, approximately half were refractory to both fludarabine and alemtuzumab and the other patients were refractory to fludarabine and considered inappropriate for alemtuzumab due to bulky disease of the lymph nodes. An objective response rate of approximately 50% consisting of 30 partial responses was achieved in the fludarabine and alemtuzumab refractory group and an objective response rate of approximately 44% was achieved in the fludarabine refractory group including 1 complete response and 34 partial responses. In this study, ofatumumab was generally well tolerated by the patients. The most frequently reported adverse events (>15% frequency) were pyrexia, diarrhea, fatigue, cough, neutropenia, anemia and pneumonia. There were no unexpected safety findings. Studies clearly indicate monoclonal antibodies (mAbs) play an important role in the treatment of CLL. Anti-CD20 mAbs with a low toxicity can be applied advantageously in subjects who cannot tolerate highly toxic treatments (i.e. advanced age), in combination with chemotherapy and as maintenance treatment. Ofatumumab preclinical data demonstrates superior CDC activity in CLL compared to rituximab. Based on this, therapeutic combinations that may exploit the enhanced CDC potential would be hypothesized to improve outcome.

2.4 Fresh Frozen Plasma (FFP)

FFP is the fluid portion of one unit of human blood that has been centrifuged, separated, and frozen solid at -18°C (-0°F) or colder within eight hours of collection. FFP contains the labile as well as stable components of the coagulation, fibrinolytic and complement systems. In addition, fats, carbohydrates and minerals are present in concentrations similar to those in circulation. Although well-defined indications exist for the use of FFP in single or multiple coagulation deficiencies, indications for many of its other uses may be empiric. These indications generally are limited to the treatment of deficiencies of coagulation proteins for which specific factor concentrates are unavailable or undesirable. In addition, circumstances exist in which FFP has been employed and is believed to be of therapeutic value, but data supporting its efficacy are limited or unavailable (e.g., multiple coagulation protein deficiencies in the uncontrollably bleeding patient). Because such patients are often critically ill and satisfactory alternative therapy may not be at hand, FFP may be appropriate. FFP is efficacious for treatment of deficiencies of factors II, V, VII, IX, X, and XI when specific component therapy is neither available nor appropriate. FFP is also a rich source of complement proteins and previous studies have demonstrated effective replacement in patients with hereditary complement deficiencies, autoimmune disease and cancer. Complement is crucial for the physiological processing of immune complexes and the beneficial effect of reconstituting the deficient complement component is likely to be at least in part the result of temporarily restoring this biological role. Evidence to support this includes the demonstrations that: (i) the uptake of immune complexes by the spleen is absent in complement C2 deficiency but restored after the administration of FFP; and (ii) circulating levels of immune complexes fell in a C2-deficient individual following plasma infusion [Rudmann, 2005].

2.5 Rationale

While there have been significant advances in the understanding of the pathogenesis of CLL and innovative new strategies are being explored, few have resulted in a significant change in the survival. The vast majority of patients with this disease are elderly and often they cannot tolerate standard multi-agent chemotherapeutic or biochemotherapeutic approaches. Based on this, less toxic and more effective treatment options are needed. Ofatumumab has proven to be effective in patients with relapsed and/or refractory CLL. A phase II study found that patients treated with ofatumumab that were refractory to fludarabine and alemtuzumab had an overall response rate of 42% with a median duration

of response of 6.5 months. While this is a significant improvement in this patient population, improvements in efficacy without substantially increasing toxicity are needed. Previous studies have shown that ofatumumab is more effective than rituximab at activating complement and utilizing complement-dependent cytotoxicity (CDC) [Pawluczkowycz, 2008]. It has been also shown that patients with CLL are complement deficient, especially those that are heavily pretreated [Varga, 1995I, Schlesinger, 1996]. While not thoroughly examined, it is hypothesized that complement levels drop even lower after treatment with large doses of humanized antibodies. Based on this principle, a previous study gave 5 highly refractory CLL patients two units of FFP (as a source of complement) with rituximab (375 mg/m²) as a single agent, repeated every 1-2 weeks, as needed. All 5 patients had a “rapid and dramatic clinical and laboratory response.” In fact, 3 of the patients were rituximab refractory [Kelpfish, 2008]. Toxicity was minimal and the treatment was well-tolerated in all cases. Based on these principles, we propose treating relapsed/refractory CLL patients with FFP in combination with ofatumumab.

3.0 SUBJECT SELECTION

3.1 Number of Subjects

Subjects who meet all the following inclusion/exclusion criteria will be eligible for enrollment into the study. Approximately 42 subjects will be screened to obtain 12 evaluable subjects (assuming 15 % screen failure and 5 % drop out rates).

3.2 Inclusion Criteria

Subjects eligible for enrollment in the study must meet all of the following criteria:

1. Patients must have a pathological diagnosis of B-cell CLL
2. Patients must have received prior rituximab therapy and must have recovered from all non-hematologic toxicities. (Previous radiation is allowed as long as patients have recovered from all treatment related toxicities)
3. Patients must meet the following laboratory values:
 - Hgb \geq 9.0 g/dl
 - Platelets \geq 50,000/mm³
 - Creatinine \leq 2.0 times the institutional upper limit of normal
 - SGOT/SGPT \leq 2.5 times the institutional upper limit of normal (unless due to disease involvement of liver)
 - Total Bilirubin \leq 1. 5 times the institutional upper limit of normal
 - Alkaline phosphatase \leq 2.5 times upper limit of normal (unless due to disease involvement of the liver or bone marrow)
4. Patients must be at least 18 years of age.
5. Patients must have a performance status of 0-2 by ECOG criteria (see Appendix I).

6. All patients must be informed of the investigational nature of this study and must sign and give written consent in accordance with institutional and federal guidelines.

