3.3 Exclusion Criteria

Subjects meeting any of the following criteria must not be enrolled in the study:

1. Subjects who have current active hepatic or biliary disease (with the exception of patients with Gilbert's syndrome, asymptomatic gallstones, liver metastases or stable chronic liver disease per investigator assessment).
2. Having received rituximab within the prior 2 months
3. Treatment with any known therapeutic or experimental therapy within 4 weeks prior to enrollment, or currently participating in any other interventional clinical study
4. Other past or current malignancy. Subjects who have been free of malignancy for at least 5 years, have a history of completely resected non-melanoma skin cancer, successfully treated in situ carcinoma, adequately treated basal or squamous cell skin cancer, adequately treated Stage I or II cancer from which the patient is currently in complete remission, or any other cancer for which the patient has been disease-free for 5 years are eligible.
5. Prior treatment with anti-CD20 monoclonal antibody or alemtuzumab within 2 months prior to start of therapy.
6. Chronic or current infectious disease requiring systemic antibiotics, antifungal, or antiviral treatment such as, but not limited to, chronic renal infection, chronic chest infection with bronchiectasis, tuberculosis and active Hepatitis C.
7. History of significant cerebrovascular disease in the past 6 months or ongoing event with active symptoms or sequelae
8. Known HIV positive
9. Clinically significant cardiac disease including unstable angina, acute myocardial infarction within six months prior to randomization, congestive heart failure (NYHA III-IV), and arrhythmia unless controlled by therapy, with the exception of extra systoles or minor conduction abnormalities.
10. Significant concurrent, uncontrolled medical condition including, but not limited to, renal, hepatic, gastrointestinal, endocrine, pulmonary, neurological, cerebral or psychiatric disease which in the opinion of the investigator may represent a risk for the patient.
11. Positive serology for Hepatitis B (HB) defined as a positive test for HBsAg. In addition, if negative for HBsAg but HBcAb positive (regardless of HBsAb status), a HB DNA test will be performed and if positive the subject will be excluded. HBsAg negative, HBsAB negative, HBsAB positive subjects can be included, * See Monitoring criteria for HBcAb+ and HBV DNA negative subjects on next page.

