7.3 Safety Assessments

7.3.1 Liver chemistry stopping and follow-up criteria

Liver chemistry stopping and follow-up criteria have been designed to assure subject safety and evaluate liver event etiology. The sponsor-investigator will review all events which meet liver chemistry stopping criteria to determine if the event was due to:

- tumor lysis, disease related liver involvement
- other identified cause and to exclude drug induced liver injury (DILI) due to ofatumumab

The criteria are relevant for all Ofatumumab studies because transient elevations in LFTs may be due to tumor lysis which is of clinical benefit, disease related liver involvement or due to other chemotherapy rather than drug induced liver injury from ofatumumab.

If the event is determined to be due to causes other than ofatumumab DILI and improvement is observed after withdrawal of ofatumumab, rechallenge may be attempted if deemed appropriate by the sponsor-investigator and in addition to consent of the subject.

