7.3.1.1 Liver chemistry interruption/stopping criteria

1. ALT $>3\times\text{ULN}$ **and** bilirubin $> 2 \times \text{ULN}$ ($>35\%$ direct bilirubin; bilirubin fractionation required*)
2. ALT $>8\times\text{ULN}$
3. ALT $>5\times\text{ULN}$ for more than 2 weeks

***NOTE:** If serum bilirubin fractionation not immediately available, study drug should be discontinued if ALT $> 3 \times \text{ULN}$ and bilirubin $> 2 \times \text{ULN}$. Serum bilirubin fractionation should be performed if testing is available. If testing is unavailable, record presence of detectable urinary bilirubin on dipstick, indicating direct bilirubin elevations and suggesting liver injury.

When any of the liver chemistry stopping criteria is met, do the following:

- Immediately stop study treatment
- Hold Ofatumumab for two weeks, repeat liver chemistry testing at least twice weekly, and report to sponsor-investigator to discuss the possibility of re-challenging with ofatumumab. *Note: The 2 week time point for stopping medication was chosen because it will distinguish from LFT elevations due to tumor lysis which should have resolved within this time period. Medication is interrupted and it is a clinical and patient decision if ofatumumab may be re-started. The risk: benefit ratio is different in an oncology setting and an efficacious therapy may be life-saving.*
- Report SAE to Novartis within 24 hours

- All events of ALT > 3xULN **and** bilirubin > 2xULN (>35% direct bilirubin) (or ALT>3xULN and INR>1.5, if INR measured; INR measurement is not required and the threshold value stated will not apply to subjects receiving anticoagulants), termed 'Hy's Law', **must be reported as an SAE (excluding studies of hepatic impairment or cirrhosis).**
- NOTE: if serum bilirubin fractionation is not immediately available, study treatment should be discontinued if ALT > 3xULN **and** bilirubin > 2xULN. Serum bilirubin fractionation should be performed if testing is available. If testing is unavailable, **record presence of detectable urinary bilirubin on dipstick**, indicating direct bilirubin elevations and suggesting liver injury.

Liver chemistry follow-up assessments are to be followed until liver chemistries resolve, stabilize or return to baseline values.

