7.4.4 Laboratory and Other Safety Assessment Abnormalities Reported as AEs and SAEs

- Any abnormal laboratory test results (hematology, clinical chemistry, or urinalysis) or other safety assessments (e.g., ECGs, radiological scans, vital signs measurements), including those that worsen from baseline, and felt to be clinically significant in the medical and scientific judgment of the investigator **are** to be recorded as AEs or SAEs.
- All events meeting liver stopping criteria must be recorded as an SAE.
- However, any clinically significant safety assessments that are associated with the underlying disease, unless judged by the investigator to be more severe than expected for the subject's condition, are **not** to be reported as AEs or SAEs.
- B cell depletion, IgG below LLN, low CD19+ count, and hypogammaglobulinemia due to treatment with ofatumumab are **not** to be reported as AEs or SAEs.

- Infusion related AEs may lead to a prolonged infusion time. Overnight stay at the hospital due to slow infusion rate is **not** to be reported as a SAE.

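### The liver-involvement waiver at entry has no ALT cap, while stopping criteria 2 and 3 ignore baseline, so an unchanged ALT can force an interruption and an SAE report

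*Combined protocol and SAP*

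**What the plan says.** **Entry.** Section 3.2, item 3, allows SGOT/SGPT up to 2.5 "times the institutional upper limit of normal (unless due to disease involvement of liver". Nothing replaces the limit when the exception applies. Total bilirubin is limited to 1.5 × ULN, and that limit carries no exception.

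**Stopping.** Section 7.3.1.1 lists three criteria: (1) ALT above 3 × ULN together with bilirubin above 2 × ULN; (2) ALT above 8 × ULN; (3) ALT above 5 × ULN for more than 2 weeks. Meeting any one leads to "Immediately stop study treatment", a two-week hold, and an SAE report to the drug supplier within 24 hours. None of the three is set relative to baseline. The same section calls this an interruption and leaves restart to the clinician and the patient.

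**Cause review and restart.** Section 7.3.1 has the sponsor-investigator judge whether an event that met a criterion came from tumor lysis, liver involvement or the drug. If the drug is not the cause and "improvement is observed after withdrawal of ofatumumab, rechallenge may be attempted". Section 7.3.1.2 allows restart after the hold if the treatment is showing benefit and the patient wishes to continue.

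**Recording.** Section 7.4.4, second bullet: "All events meeting liver stopping criteria must be recorded as an SAE". Its third bullet takes "any clinically significant safety assessments that are associated with the underlying disease" out of AE and SAE reporting unless they are worse than expected. Section 7.4.1 makes the same exemption in the definition of an AE.

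**The concern.** The entry rule admits patients whose ALT is high because CLL is in the liver. The stopping rule does not distinguish that ALT from one that rose on treatment. A stable baseline value can then interrupt dosing during the weekly phase and start expedited reporting, although nothing has happened to the patient since screening.

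Two things are at stake. First, a patient admitted on purpose may be interrupted, and the restart wording does not fit that patient well. Second, toxicity is a secondary endpoint. Because the recording rules can be read in two ways, the same ALT could be entered as an SAE for one patient and not entered for another.

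**Working it through.** The plan gives no figure to reproduce. The check sets the thresholds side by side.

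**Inputs, in multiples of ULN**
- Entry ALT (SGPT): at most 2.5, or no limit under the waiver (3.2, item 3).
- Entry bilirubin: at most 1.5, no waiver (3.2, item 3).
- Criterion 1: ALT > 3 and bilirubin > 2. Criterion 2: ALT > 8. Criterion 3: ALT > 5 for > 14 days (7.3.1.1).

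**Step 1: without the waiver.** The highest entry ALT is 2.5. The lowest ALT in any stopping criterion is 3. Since 2.5 < 3, no eligible patient meets a criterion at the entry values.

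**Step 2: with the waiver.** ALT has no ceiling.
- Criterion 2 is met by any ALT above 8, for example a stable 9.
- Criterion 3 is met by any ALT above 5 that lasts more than 14 days, for example a stable 6.
- Criterion 1 needs bilirubin above 2, but entry allows at most 1.5, so it is not met at the entry values.

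A grid confirms this. It used ALT from 0.5 to 20 and bilirubin from 0.2 to 3.0 in steps of 0.1, with durations of 0, 1, 2 and 3 weeks. Without the waiver, 21 × 14 × 4 = 1,176 combinations are eligible and none meets a criterion. With it, 196 × 14 × 4 = 10,976 are eligible. Criterion 2 is met from ALT 8.1 upward, criterion 3 from 5.1 upward at 3 weeks, and criterion 1 never. The overlap comes from the waiver alone. The counts describe the grid and say nothing about how many patients are affected.

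**Step 3: timing.** Criterion 2 has no duration, so the first value examined under the stopping rule suffices. For criterion 3, weekly dosing puts doses 1, 2 and 3 on days 1, 8 and 15. Day 15 is 15 − 1 = 14 days after dose 1, which is not more than 2 weeks. Meeting criterion 3 by dose 2 or 3 on schedule therefore requires pre-treatment time to count, and the text does not say whether it does.

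**Step 4: after the trigger.**
- Cause review under 7.3.1 begins only once a criterion has been met, so attribution to CLL does not prevent the stop.
- The rechallenge wording in 7.3.1 presumes that ALT improves off the drug. An elevation caused by the disease under treatment need not do so.
- Section 7.3.1.1 justifies the two-week hold by the time in which tumor lysis should clear. That reason does not cover a stable elevation.
- The restart wording in 7.3.1.2 presumes benefit, which is not defined and cannot exist before any dose.
- Follow-up may end when values level off or are back at baseline (7.3.1.1). A patient stable at 9 × ULN satisfies that while still meeting criterion 2. Section 7.3.1.2 applies the criteria at any time, so the trigger can recur after restart.

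**Step 5: recording.** For a stable, disease-driven ALT of 9 × ULN, 7.3.1.1 and the second bullet of 7.4.4 say SAE. Section 7.4.1 and the third bullet of 7.4.4 say neither AE nor SAE, unless it is more severe than expected.

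**The case against.** **Other entry filters.** Exclusion 1 in Section 3.3 bars active hepatic disease, and exclusion 10 bars uncontrolled hepatic disease that the investigator considers a risk. A patient at 9 × ULN must pass both. This narrows the overlap without closing it. Exclusion 10 rests on judgment. Exclusion 1 excepts "liver metastases or stable chronic liver disease per investigator assessment" and does not say on which side CLL in the liver falls.

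**Deliberate caution.** Section 7.3.1 names liver involvement as a possible cause, so fixed thresholds followed by review may be intended. That is a defensible design, but the plan does not say that it applies to a value already known and accepted at entry.

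**The SAE rules may not conflict.** The third bullet of 7.4.4 opens as a qualification and can be read as an exception to the second. Section 7.4.1 also leaves out pre-existing conditions that fluctuate without worsening. This is a fair reading, and it weakens any claim of flat contradiction within 7.4.4. It does not settle the matter, because the second bullet admits no exception and 7.3.1.1 repeats the SAE instruction without one.

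**Stronger readings that a reader might infer**
- *Permanent removal from treatment.* Not supported: 7.3.1.1 describes an interruption with restart possible.
- *A stop before the first dose.* This is an inference. Liver tests are drawn pre-treatment (7.1) and SAE reporting starts at consent (7.4.6), but stopping and withdrawal presuppose that dosing has begun.
- *A lower intent-to-treat response rate.* Not shown. It would require that the patient would have responded and that the hold costs the response. A 14-day hold spans two weekly dosing intervals, but the plan does not say whether held doses are omitted or delayed.
- *An inflated toxicity endpoint.* Sections 8.1 and 8.4 tabulate toxicity by type and severity, and the monitoring flag uses grade, not the SAE count. The effect is on which liver events are recorded as SAEs.

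**Conclusion.** The point holds in a limited form. Under the waiver, one unchanged ALT can satisfy both the entry rule and stopping criterion 2 (above 8 × ULN), or criterion 3 (above 5 × ULN for more than 2 weeks). Each such patient faces a mandatory two-week interruption and an SAE instruction that other parts of the protocol appear to lift. Criterion 1 is not part of the problem at the entry values.

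This assumes that exclusions 1 and 10 do not remove the patient, that the elevation is attributed to CLL in the liver, and that the criteria are applied as written, without regard to baseline. The documents do not say how many patients would have liver involvement with ALT at these levels. The number cannot be derived and is probably small. No bias in the response rate is claimed. The wording should be corrected, but the point does not threaten the trial's main conclusion.

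**What to change.** 1. Reconcile Section 3.2, item 3, with Sections 7.3.1, 7.3.1.1 and 7.3.1.2. State how an ALT elevation present at baseline and due to liver involvement is handled under the stopping, rechallenge and restart wording, and whether pre-treatment time counts for criterion 3. The clinical rule is for the sponsor to choose.
2. Reconcile Sections 7.3.1.1, 7.4.1 and 7.4.4 so that one rule says whether such a value is an SAE.
3. In the safety tables of Section 8.4, report liver events as treatment-emergent relative to the screening value, so that an unchanged baseline elevation can be told apart from a rise on treatment.

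The cost is wording changes and slightly more tabulation. No new tests are needed, because liver chemistry is already collected at screening.
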